Serious adverse events (SAEs), as defined by the FDA, will be evaluated at each visit. Any SAE, whether or not related to study medication, will be reported to the IRB within 24 hours. The initial SAE report will be followed by submission of a completed SAE report within 2 days. In the event that a patient either withdraws from the study or the investigator decides to discontinue a patient due to SAE, the patient will have appropriate follow-up medical monitoring. Monitoring will continue until the problem requiring hospitalization has resolved or stabilized with no further change expected, is clearly unrelated to study medication, or results in death. The outcome of SAEs will be periodically reported to IRB.

Inclusion of Women

The subjects will include only females, ages 18-45 years old, from various race/ethnic backgrounds, as reflected in the local community in the greater Houston area.

Inclusion of Minorities

Our study will include minority groups in proportions that will be representative of the ethnic/racial composition of the local community in Houston, Texas. Our projected numbers for minority enrollment are detailed in the enrollment table attached.

Inclusion of Children

Children will not be included in the study. The inclusion of children at this early stage would increase substantially the number of subjects needed for the overall project and would not be conducive to the perinatal nature of the study. At this time, we will focus on an adult population (ages 18-45 years old).

Prisoners and pregnant women

We are aware of the special protections afforded to prisoners per federal regulations. We will not actively recruit people who are incarcerated to participate in this study. We do, however, acknowledge the possibility of research participants in our target population being incarcerated during the study. If an active participant is incarcerated for an extended period of time, disenrollment from the study will be necessary. No research interaction or intervention will take place until an incarcerated participant is released from jail. Finally, neither the pregnant woman nor neonates will be enrolled in this study. Women will only be recruited postpartum and after having weaned their child.

DATA ANALYSIS PLAN - General Data Analysis: The data analytic strategy will use generalized linear modeling. Statistical analyses will use SAS v.9.3. Preliminary data analyses will inspect baseline, treatment from baseline differences as well as correlations between baseline variables and specified outcomes. Baseline characteristics will be compared within groups using Student's t-tests for continuous data and chi-square tests for categorical data.

Sample size justification: our power calculation is guided by a previous study - intravenous ketamine in TRD patients (28) with effect size (Cohen's $d = 1.46$) or Brexanolone in PND (effect size 1.2) (12, 32). For an effect size 1.2, a total of 10 PND patients will be required for within-subject design with probability 95 % that the study will detect a treatment difference at a one-sided 0.05 significance level.

Hypothesis: Based on previous studies (33, 34) and our pilot Ketamine TRD patient data, we predict that ketamine infusion compared to baseline will significantly decrease HAM-D scores in PND patient at 24 hrs. The severe anxious subtype will have prominent improvement.

Analysis: We will use linear regression to assess associations between improvements in depressive symptoms (change in the HAM-D from baseline using LOCF). A paired t-test was performed to evaluate the key efficacy measure - change from baseline in HAMD total score. We will also perform a secondary analysis comparing change from baseline to endpoint using last observation carried forward (LOCF) using a paired sample t-test. Secondary outcomes are safety and tolerability measures, including treatment-emergent AEs and changes from EPDS, GAD-7, PHQ-9, and C-SSRS. We will also investigate specific markers for treatment response.

Alternate plans: The proposal applies the widely used ketamine sub-anesthetic dose (0.5 mg/kg) as a treatment for PND. If the effect is less clear or patient experiences any adverse effects, alternate strategies will be explored (two doses of ketamine instead of single or low dose 0.3 mg/kg if adverse effects etc. respectively). Patient safety and tolerability will be the most important guiding principle. This will require an amendment in the protocol and an updated consent.

JUSTIFICATION - Research in PND is of critical importance due to its substantial burden on mother, family and child's emotional, cognitive and behavioral development. Rapid and effective treatment of severe PND is a significant unmet need. The primary goal of the project is to evaluate the safety and efficacy of sub-anesthetic antidepressant dose ketamine treatment in severe PND patients. This proposal will be the first systematic investigation of ketamine's antidepressant effect in PND. The study design is simple and robust that can provide

early treatment response signal without significant additional discomfort for patients. The results from this pilot proposal could potentially yield critical information regarding markers of treatment response in PND - a potentially high impact research area. the

Having a placebo group in this research project would not be warranted at this place since the aim is to determine if a lower ketamine dose would be as effective and with lower side effects for PND patients.

Data Handling and Record Keeping

This study will acquire, use and create individually identifiable health information (known as Protected Health Information or PHI). Confidentiality will be protected at all times by having research records identified by code number only. All research information will be stored in locked files at all times. Only authorized research staff will have access to the information gathered in this study. Only subjects capable of providing consent will be included in the study.

As per the Health Insurance Portability and Accountability Act (HIPAA), all individuals who are eligible and agree to participate in this research study will be required to sign a HIPAA research authorization prior to participation. If an individual refuses to sign the HIPAA research authorization, they will not be able to participate in this study. The HIPAA form is part of the official consent form.

Data will be stored separately from the participants' identifiers. Both will be stored on encrypted drives on computers in locked offices. Confidentiality will be protected by having research records identified by code number only. All research information will be stored in locked files at all times. Only authorized research staff will have access to the information gathered in this study. All paper data will be stored on the 3rd floor of the UT Department of Psychiatry, at the BBSB (room number 3260) in a double-locked cabinet. The electronic data will be stored on the L drive, in a subfolder labeled "BPRC", located under the subfolder "UT Center of Excellence on Mood Disorders". An Accounting of Disclosure (AOD) will be created and maintained for any disclosure of individually identifiable information (III) outside the UTHSC-H. The manual spreadsheet will include the date of the disclosure, nature or description of the III disclosed the purpose of each disclosure and the name and address of a person or agency to which the disclosure was made.. Strict monitoring of hemodynamic and respiratory changes as well as psychiatric screening will be performed during each infusion of ketamine.

Ethics

IRB approval will be sought from CPHS for the University of Texas Health Science Center at Houston. Written informed consent will be obtained directly from the subject. Privacy and confidentiality will be maintained with a special number to be used to identify the subject in the study and only the investigator and his research staff will know their name.

Quality control and assurance

No plans to have ongoing third-party monitoring. However, we will conduct routine (bimonthly) reviews of consistency, reliability, and accuracy of data collected for any paper records. Similar checks for any data in electronic form will also be conducted but in an automated fashion (e.g checking for accurate time/date stamps, file sizes etc.).

Publication Plan

We plan to present preliminary versions of the findings at conferences during the first and second year. Definitive publication of findings will occur in the 6-12 months following the end of the two-year award period.

REFERENCES

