breastfeeding mother and the baby. Ketamine and its metabolites will be evaluated in PND patients receiving ketamine 0.5 mg/kg or 0.2 mg/kg at 30 mins, 2 hours and 4-5 hrs after ketamine infusion. All adverse medical and psychiatric events with onset or worsening after the administration of ketamine will be included in the analysis.

The proposed experiment will be a proof-of-concept study in which we will evaluate the safety, pharmacokinetics, and efficacy of ketamine 0.5 mg/kg and 0.2 mg/kg over 40 minutes in a double-blinded and crossover fashion separated over one week (5) (dose used in antidepressant clinical trials) in PND patients who are not currently breastfeeding. The primary outcome measure of efficacy will be the Hamilton Depression Rating Scale (HAM-D-17) at 24 hours and additional secondary anxiety and mood scales. (6). Any adverse medical and psychiatric events will be recorded and summarized. Ketamine and its metabolites will be evaluated at 30 mins, 2 hours and 24 hrs.

Hypothesis 1): Ketamine will significantly decrease (>50%) in HAM-D17 scores at 24 hrs after infusion from baseline. The 0.5 mg/kg dose will be more efficacious than 0.2 mg/kg in improving depression symptoms.

Hypothesis 2) Ketamine will improve anxiety symptoms in PND (as measured using HAM-Anxiety and EPDS) at 24 hrs after infusion in patients with PND. Anxious subtypes are the most common subtype during a late postpartum period representing about 70 % of PND. (40)

Hypothesis 3) Ketamine infusion will be tolerated well by the patients with fewer side effects at 0.2 mg/kg compared to 0.5 mg/kg.

METHODS

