Research Design and Methods: All human subjects' research will be conducted with full approval from the IRB at the University of Texas Health Science at Houston. We will recruit PND patients (N=10) who will be administered a single intravenous infusion of Ketamine either at 0.5 mg/kg or 0.2 mg/kg over 40 minutes in a double-blinded and crossover fashion separated by minimum 7 days, with the order being randomized and balanced across subjects. Two doses will help decide the safe, tolerable and effective dose for PND subjects will undergo a standard screening interview visit to confirm eligibility evaluations including SCID-4 interview (27) and collection of demographic, clinical and medical history. To ensure medical stability, each patient will have a physical examination and urine toxicology screen to rule out the recent undisclosed use of illicit substances. It will also be requested that the patient provide a record of lab results to indicate adequate health for inclusion.

We will pre-screen potential participants over the phone to minimize the invitation to non-eligible participants. Eligible patients that want to participate in the study will be scheduled to have a screening visit to review consent and determine eligibility.

The total duration of the commitment of the study is minimum of 4 weeks. Extension of the timeline can occur depending on the time between the screening visit and the first infusion dose. The total commitment should not exceed 3 months. There will be a minimum 7 days between the 2 infusions. Patients who qualify will complete the infusions on another day at UTHealth Clinical Research Unit at Memorial Hermann-TMC, Houston. University of Texas Health Science Center at Houston Memorial Hermann-TMC [name] or at our Harris County Psychiatric Center (HCPC) where they will be given the ketamine infusion by the study nurse. Patients will be advised to follow the American Association Preoperative Fasting Guidelines prior to infusion.

There will be two appointments where they will be administered a single intravenous infusion of Ketamine either at 0.5 mg/kg or 0.2 mg/kg over 40 minutes in the first infusion visit and a second infusion visit where they will receive the infusion that was not given on the first visit, where there will be a minimum of 7 days between infusions.

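### Hypothesis 3 claims fewer side effects at 0.2 than at 0.5 mg/kg in the same women, but the plan states no dose contrast for adverse events

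*Combined protocol and SAP*

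**What the plan says.** Hypothesis 3, under Primary Hypotheses and Specific Aims, reads "Ketamine infusion will be tolerated well by the patients with fewer side effects at 0.2 mg/kg compared to 0.5 mg/kg". The Methods give the design as a "double-blinded and crossover fashion separated by minimum 7 days, with the order being randomized and balanced across subjects", so each woman supplies both halves of that comparison. The Justification section declines a placebo group because the purpose is to "determine if a lower ketamine dose would be as effective and with lower side effects for PND patients".

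Three statements govern AEs in the analysis:
- Aims: "All adverse medical and psychiatric events with onset or worsening after the administration of ketamine will be included in the analysis".
- Aims: "Any adverse medical and psychiatric events will be recorded and summarized".
- Data Analysis Plan, Analysis paragraph: "Secondary outcomes are safety and tolerability measures, including treatment-emergent AEs".

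The only paired method is for depression scores: "A paired t-test was performed to evaluate the key efficacy measure - change from baseline in HAMD total score", with a secondary version using last observation carried forward. Both compare a score with baseline, not one dose with the other.

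Collection is tied to the infusions. The assessment schedule marks an AE report after infusion 1, after infusion 2 and at the follow-up calls. Research Design and Methods describes calls that ask about AEs on day 1 after the first infusion, and on days 1 and 7 after the second. Medical Monitoring gives days 1, 2 and 7 after infusion.

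**The concern.** Tolerability is half of the dose question that the trial is meant to inform, and the crossover was chosen so that each woman is her own control. The plan does not carry that comparison into the analysis of AEs. It does not say what is counted (women with any event, events per woman, severity), over what window, for which infusion, or how the doses are contrasted.

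Both infusions are ketamine, so an inclusion rule based on onset or worsening after ketamine does not by itself separate the doses. The uneven contacts add to this. Under Research Design and Methods, whichever dose comes second has an extra day-7 call. Balanced order limits the resulting bias between doses, but does not remove the noise or the uncertainty about events reported between the first day-1 call and the second infusion.

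At stake is whether a small difference in raw counts among 10 women is read as support for Hypothesis 3 with nothing to show how easily chance produces it.

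**Working it through.** **1. The plan's own figure.** Sample size justification: d = 1.2, within-subject, one-sided 0.05, 95% power, N = 10. For a paired t-test, power is P(T > t(0.95; n−1)), with T noncentral t and noncentrality d√n. At n = 10 the noncentrality is 1.2 × √10 = 3.79 and power is 0.9675; at n = 9 power is 0.9484. Ten is the smallest n that reaches 95%, so the figure reproduces. It rests on an antidepressant effect size. Nothing sizes the AE comparison.

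**2. What Hypothesis 3 needs, against what is written.**

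| Needed | In the documents |
|---|---|
| AE report after each infusion | Yes (assessment schedule, Methods) |
| Rule attributing an event to an infusion | Not stated; can be derived from date and randomisation code |
| Same window after both infusions | No; contacts differ, and two sections disagree |
| AE measure | Not stated |
| Dose contrast, paired or not | Not stated |
| Interval or other measure of uncertainty | Not stated |

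**3. How often chance alone looks like support.** Inputs are the rates in the risk section: 58.3, 54.2, 50.0 and 45.8%, plus 35% as the middle of 30-40% for headache. (Drowsiness appears there as both 48.5% and 45.8%; the second is used.) Applying these rates to 0.5 mg/kg is an assumption. Suppose the doses do not differ.
- One side effect, doses independent, X and Y both Binomial(10, p): P(X − Y ≥ 2) is 24% at p = 0.35 and 25% at p = 0.50. So 0.2 mg/kg shows at least two fewer women about a quarter of the time.
- Sum of all five side effects: the total is lower at 0.2 mg/kg in about 46% of 20,000 simulated trials. The rest are ties or go the other way.

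**4. What a within-woman estimate would give.** The documents give no rates for 0.2 mg/kg, so half and three quarters of the 0.5 mg/kg rates are assumed.
- Mean count at 0.5 mg/kg: 0.583 + 0.542 + 0.500 + 0.458 + 0.350 = 2.433 per woman. The expected difference is 0.5 × 2.433 = 1.22 at half rates and 0.25 × 2.433 = 0.61 at three-quarter rates.
- If all events are independent, the variance of the difference is Σp(1−p) over both doses. At half rates this is 1.217 + 0.913 = 2.130 (SD 1.46); at three-quarter rates, 1.217 + 1.141 = 2.358 (SD 1.54).
- Allowing for period with five women per order leaves 8 df (t = 2.306). The 95% half-width is 2.306 × 1.46/√10 = 1.06 at half rates and 2.306 × 1.54/√10 = 1.12 at three-quarter rates.
- An average result would then be 1.22 (0.16 to 2.28) at half rates, or 0.61 (−0.51 to 1.73) at three-quarter rates.

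**5. Sensitivity to clustering.** Simulated one-sided power of a paired t-test on counts, n = 10, 20,000 trials, without period adjustment:

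| Correlation between side effects | Half rates | Three-quarter rates |
|---|---|---|
| None | 0.78 | 0.31 |
| Woman effect shared by both doses, 0.3 | 0.84 | 0.35 |
| Woman effect shared by both doses, 0.5 | 0.89 | 0.40 |
| Within an infusion, 0.3 | 0.58 | 0.22 |
| Within an infusion, 0.5 | 0.49 | 0.19 |
| Woman 0.2 plus infusion 0.3 | 0.59 | 0.23 |

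With clustering within an infusion, two-sided power at half rates is 0.35-0.44. With equal rates the test rejects about 5% of the time, as it should.

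**The case against.** The best defence is that the data are sound and the study is small. AE reports and calls follow each infusion, the infusions are at least 7 days apart, and date plus randomisation code gives the dose. The listed side effects are reported for the 4 hours after an infusion, so few should straddle both. Summarising does not exclude summarising by dose, AEs are also to be included in the analysis, and the general strategy of generalized linear modeling can handle counts. A descriptive by-dose table is a legitimate choice in a proof-of-concept study of 10 women.

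Much of this stands, and it rules out three stronger readings that a reader might infer:
- That AEs are collected without regard to dose, so the trial cannot address Hypothesis 3. The schedule contradicts this.
- That an event starting after the first infusion and worsening after the second belongs to neither dose. It meets the onset-or-worsening rule at both; what is missing is an attribution rule.
- That the plan relies on a nearly powerless yes/no test of women with any AE. No such test is proposed.

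The power figures also cannot carry the argument, since the rates at 0.2 mg/kg are assumed and the result moves widely with clustering.

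What the defence does not supply is the contrast itself. A comparative hypothesis in a crossover needs a stated comparison, and neither a general modelling strategy nor the word for a summary provides one.

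**Conclusion.** The concern holds as a gap in the analysis, not in the data. The plan states a directional dose claim about side effects and specifies no dose contrast, AE measure, common window or interval with which to assess it. Followed as written, the claim could rest on raw counts that favour 0.2 mg/kg in nearly half of trials when there is no difference.

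The 46% rests on the risk-section rates applying equally at both doses; it is close to one half for any such rates, because only ties keep it below that. How precise the better analysis would be is uncertain: about 49-89% one-sided power at half rates and 19-40% at three-quarter rates, depending on assumed rates and clustering. These ranges argue for estimation and not for a formal test of Hypothesis 3. The change is worth making before unblinding, but the omission does not threaten the trial's conduct or its depression analysis.

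**What to change.** Add to the Analysis paragraph of the Data Analysis Plan:
- Attribute each AE, by onset or worsening, to the most recent infusion.
- For the dose comparison, count AEs per woman per infusion over the same window after both infusions, up to the day-1 call. Both accounts of follow-up include that call.
- Report the within-woman difference in count (0.5 minus 0.2 mg/kg) with a confidence interval, allowing for period, and label it as estimation. Give a signed-rank test as sensitivity.
- Tabulate all AEs descriptively by dose and severity, including serious events and those after day 1. A count treats mild and serious events alike, and this table restores the distinction.

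Reconcile the follow-up contacts in Research Design and Methods with those in Medical Monitoring.

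The cost is a few sentences and one more table, with no new data or patients. The downside is a wide interval with 10 women, so the tolerability claim may read weaker than a table of raw counts would suggest.

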Before the infusion, the psychiatrist and anesthesiologist will evaluate the patient. During the infusion, patients will be asked constantly about "how they feel" and will be monitored continuously by the registered nurse under the supervision of an Anesthesiologist. EKG and pulse-oximetry will be monitored throughout the procedure to

check for hemodynamic changes. After the completion of 40 min infusion, patients will rest for two-four hours under the observation of clinical nurse.. After the infusion both psychiatrist and anesthesiologist will evaluate the patient. Patients may complete clinical questionnaires after this session at HCPC or CRU for approximately 30 minutes. After the first infusion, patients will be contacted one day after over the phone and after the second infusion, patients will be contacted one day after and 7 days after the infusion. During the phone call, patients will be asked about their physical health, will be asked about adverse events and respond questionnaires that evaluate mood status.

Recruitment: The current project will ensure robust and timely recruitment through coordination with ongoing studies at the UT Center of Excellence on Mood Disorder (CEMD) ([name], Departmental Chair). [name] runs a perinatal clinic focused on pregnant or postpartum women with mood disorders in the psychiatry department. [name] also collaborates with [name], UTHealth Department of Obstetrics, Gynecology and Reproductive Sciences on a postpartum research project. Additionally, a large research participant registry has been set up by this UT center (n = 4952 over the last 5 years, of which 80% have a mood disorder history).

Recruitment will also be facilitated through the UT Research Match program. On average, 200 patients have a higher report of depression and mental health problems in the last year and of which nearly 100 patients had higher EPDS scores that meet PND criteria. The perinatal psychiatry clinic will facilitate clinical recruitment. Subject recruitment will include initial identification of cohort pool using selection criteria and subsequent review of identified patient records before final vetting and consent.

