IRB NUMBER: HSC-MS-18-0416
IRB APPROVAL DATE: 06/26/2019

Urine pregnancy test	X	X		X			
Vital Signs	X	X		X			
Height and Weight measurement	X						
Blood Collection		X	X ¹	X	X ²		
Structured Clinical Interview for DSM-IV Axis I Disorders (SCID-I)	X						
Hamilton Depression Rating Scale (HAM-D-17)	X	X	X	X	X	X	X
Montgomery-Asberg Depression Rating Scale (MADRS)	X	X	X	X	X	X	X
Edinburgh Postnatal Depression Scale (EPDS) scale	X	X	X	X	X	X	X
Young Mania Rating Scale (YMRS)	X		X		X		
Clinical global improvement (CGI)	X		X		X		
Brief Psychiatric Rating Scale (BPRS)	X		X		X		
Generalized Anxiety Disorder (GAD-7)	X	X	X	X	X	X	X
Columbia Suicide Severity Rating Scale (C-SSRS)	X		X		X		
Hamilton Anxiety Rating Scale (HAM-A)	X		X		X		
Snaith-Hamilton pleasure scale (SHAPS)	X		X		X		
Beck Depression Inventory (BDI)	X	X	X	X	X	X	X
AE Report	X		X		X	X	X
Concomitant Medications	X		X		X		
Study Contact Card given			X		X		

¹ Done at 30 minutes after infusion (+/-10), 2 hours after infusion (+/- 30 minutes) and 4.5 hours after infusion. IRB NUMBER: HSC-MS-18-0416

Patients that are unable to arrive to the appointment with a caregiver will be reimbursed for 1-2 hours of transportation to and from the infusion days. They will receive a phone call that same day to ensure safe arrival home. UTH Health IRB APPROVAL DATE: 06/26/2019

All of the above clinical questionnaires will be completed at the screening visit as well as on the ketamine infusion day, except the SCID-I, which will only be completed at the screening.

All data collected on paper forms will be stored in locked cabinets, while electronic data is stored on our secure password protected server (maintained by the UTHealth Medical School Information Technology Department). All electronic records will identify study participants only by a study code, and the electronic file linking codes to individual identifiers will be destroyed once data collection is complete.

Patients will arrive fasting from midnight on study visit day have blood draws and complete questionnaires at our clinical research suite at UTHealth's Biomedical and Behavioral Sciences building (BBSB) at [name] or at UTHealth CRU at Memorial Hermann-TMC, Houston. University of Texas Health Science Center at Houston Memorial Hermann-TMC [name] or at UT Health Harris County Psychiatric Center (HCPC)

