Placement of IV: For both of the infusion days, after the initial evaluation is done, patients will be placed one intravenous line in each arm. One line will be used for the ketamine infusion and the other line will be used for the collection of blood samples and to reduce discomfort for patients with frequent blood draws. If the sample is not obtained from the IV line due to clotting, the patient will be asked if they would like to have a blood draw using a BD Vacutainer.

Medical Monitoring: During the infusion, patients will receive continuous monitoring from the nurse and the attending and after the completion of 40 min infusion, patients will rest for two hours under the observation of clinical nurse and reassessed again by anesthesiologist/psychiatrist (advance life support trained) at 2 hours after infusion. Patients will be discharged from the hospital unit between 2-4 hours after the infusion with a responsible adult for the study visit. Patients will be contacted on days 1, 2 and 7 post-infusion for a follow-up assessment of mental state by telephone and will be scheduled for study visits.

Stopping Rules: Any worsening of depression symptoms - if patients score a 3 on item 3 of the HDRS or 3 on item 10 of the MADRS or total HDRS score (first 21-items) increases by 5 points or more from one visit to the next weekly visit. The C-SSRS will be administered to monitor suicidal ideation and behavior. Increased observation consists of daily phone calls with study physicians and/or increasing visit frequency based on the PI's clinical judgment.

Blood tests: Ketamine and norketamine plasma levels will be collected before and 30 minutes, 2 hours and 4 to 5 hours after the infusion. Samples will be stored at BBSB for analysis. Analyses will be performed by Gas Chromatograph-Mass Spectrometer (30).

Clinical measures - Clinical rating and questionnaires will be administered. Treatment response will be operationally defined as 50% improvement from baseline in the HAM-D17 scores.

POTENTIAL RISKS/DISCOMFORTS

Diagnostic procedures and questionnaires: Some of the questions asked during the screening may be considered sensitive information, including drug use history and psychiatric history. Answering these questions may be psychologically discomforting to some subjects. There are also risks associated with loss of confidentiality.

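### Hypothesis 2 is to be tested with HAM-A at 24 hours, but the schedule shows no HAM-A at the Day 1 calls; PHQ-9 is a listed secondary outcome that is never scheduled

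*Combined protocol and SAP*

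**What the plan says.** Hypothesis 2, under Primary Hypotheses and Specific Aims, reads: "Ketamine will improve anxiety symptoms in PND (as measured using HAM-Anxiety and EPDS) at 24 hrs after infusion in patients with PND". The paragraph introducing the hypotheses makes HAM-D-17 at 24 hours the primary efficacy measure and adds "additional secondary anxiety and mood scales" without naming them.

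In the schedule under Clinical and diagnostic assessments, the HAM-A row has marks at screening and in the After Infusion column of each infusion day. The sentence following the table says: "All of the above clinical questionnaires will be completed at the screening visit as well as on the ketamine infusion day", with SCID-I excepted.

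Two passages describe the telephone follow-up, and neither names a scale. Research Design and Methods says that patients will "respond questionnaires that evaluate mood status". Medical Monitoring says: "Patients will be contacted on days 1, 2 and 7 post-infusion for a follow-up assessment of mental state by telephone". Medical Monitoring also fixes the length of stay: "Patients will be discharged from the hospital unit between 2-4 hours after the infusion".

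The Analysis paragraph of the Data Analysis Plan gives the secondary outcomes as safety and tolerability measures, including adverse events and changes in EPDS, GAD-7, PHQ-9 and C-SSRS. HAM-A is not in that list.

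**The concern.** The hypothesis, the schedule and the secondary-outcome list name three different sets of measures. Site staff work from the schedule. If they follow it, one of the two instruments named in Hypothesis 2 will have no value at the time point the hypothesis specifies, and a 24-hour score that was not collected cannot be recovered later.

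The same-day rating is a poor stand-in. The risk section places the common side effects, such as feeling unreal, abnormal sensations and sleepiness, in the 4 hours after infusion, which is when the post-infusion HAM-A would be taken.

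Anxiety is also central to the rationale. The protocol puts anxious subtypes at about 70% of PND, and the analysis plan predicts prominent improvement in the severe anxious subtype. Without HAM-A, Hypothesis 2 would rest on EPDS, which the background describes as a screening tool for PND. PHQ-9 would be promised as an outcome with no data behind it.

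**Working it through.** No figure in the plan bears on this point, so the check sets the schedule against the hypothesis and counts.

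**1. Reading the columns.** The table header has 8 data columns: screening, before and after infusion on each of two days (4), the Day 1 call after infusion 1, the Day 1 call after infusion 2, and the Day 7 call after infusion 2. The rating-scale rows have only 7 cells, so one column was lost or two were merged. Two rows show where. The pregnancy-test row is marked in cells 1, 2 and 4 (screening and before each infusion). The AE row is marked in cells 1, 3, 5, 6 and 7. The first five columns are therefore intact, and cells 6 and 7 are the surviving follow-up cells.

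**2. Marks by row.**

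| Cell | Column | HAM-A | EPDS, GAD-7 |
|---|---|---|---|
| 1 | Screening | X | X |
| 2 | Before infusion 1 | – | X |
| 3 | After infusion 1 | X | X |
| 4 | Before infusion 2 | – | X |
| 5 | After infusion 2 | X | X |
| 6, 7 | Surviving follow-up calls | – | X |

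HAM-A has 3 of 7 cells; EPDS and GAD-7 have 7 of 7.

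**3. Is it a stray misreading?** Apart from SCID-I there are 11 scales. Five (HAM-D-17, MADRS, EPDS, GAD-7, BDI) are marked in all 7 cells. Six (YMRS, CGI, BPRS, C-SSRS, HAM-A, SHAPS) are marked in cells 1, 3 and 5 only. 5 + 6 = 11, with no exceptions. This looks like a deliberate short set and full set, not a slip in one row.

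**4. Which contact could supply 24 hours?** Discharge is 2-4 hours after infusion, so After Infusion is a same-day value. The only scheduled contact near 24 hours is the Day 1 call.

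**5. Coverage.** Planned infusions: 10 × 2 = 20.
- If the two Day 1 columns were merged, or the Day 7 column was lost: 0 of 20 have a scheduled 24-hour HAM-A.
- If one Day 1 column was lost and it carried a HAM-A mark: at most 10 of 20.

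**6. Baseline.** With no pre-infusion mark, screening is the only untreated HAM-A value. The consent section calls that visit screening/baseline, so it can serve for infusion 1. For infusion 2, a change from screening also spans infusion 1: "There will be a minimum 7 days between the 2 infusions".

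**7. PHQ-9.** It appears in 0 of the 12 listed instruments and 0 scheduled assessments; its only mention is in the Analysis paragraph.

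**The case against.** The best defence is that the call descriptions are general. The instrument list is introduced as a set of mood questionnaires and includes HAM-A, so questionnaires about mood status at a call could include it. The sentence after the table does not exclude other times either. It cannot, since five scales are marked at the calls. That is fair: the sentence is supporting evidence only, and the 24-hour gap rests on the table row, in a table that has lost a column. But no text names HAM-A at a call. If staff were meant to give it there, the table and text disagree and still need reconciling.

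Three further points have some force.
- The secondary-outcome list is introduced by the word including and also leaves out MADRS, BDI and SHAPS. The absence of HAM-A from it is a minor matter.
- Hypothesis 2 makes no dose comparison. A Day 1 HAM-A set against screening would answer it, so the pre-infusion ratings improve the crossover but are not strictly required by the hypothesis.
- Only one of two named measures in a secondary hypothesis of a 10-patient proof-of-concept study is affected, and PHQ-9 may be one stray word, since depression severity is covered by four other scales.

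These points limit the weight of the concern. They do not supply the missing 24-hour rating.

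**Conclusion.** The plan is wrong as written on this point. The HAM-A part of Hypothesis 2 has no scheduled 24-hour value for any of the 20 planned infusions, or for at least 10 of them on the reading of the lost column most favourable to the plan. PHQ-9 has no scheduled value at all.

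This assumes that the surviving cells were read in the right order, which the pregnancy-test and AE rows support, and that staff follow the schedule. The original table in the PDF can settle the lost column.

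The correction should be made, but the flaw is not fatal. EPDS, the other measure in Hypothesis 2, is marked in every surviving cell, as are GAD-7 and HAM-D-17. The primary analysis and the sample size do not change.

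**What to change.** Choose one of two routes.

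1. **Keep HAM-A at 24 hours.** Mark it at the Day 1 call after each infusion and before infusion (at least before infusion 2), and list HAM-A change as a secondary outcome in the Data Analysis Plan. Cost: (2 + 1) × 10 = 30 ratings at least, or (2 + 2) × 10 = 40 with both pre-infusion ratings. All fall at existing contacts. The calls get longer, with six scales instead of five. If only the Day 1 marks are added, the cost is 2 × 10 = 20 ratings, but infusion 2 then has no baseline of its own.
2. **Restate Hypothesis 2 on EPDS and GAD-7**, which are already marked before infusion and at the calls, and report HAM-A as a same-day post-infusion measure only. This adds no data collection, but it changes a pre-specified outcome, because GAD-7 is not named in the hypothesis now. It should be recorded as an amendment before any outcome data are examined. There would then be no 24-hour HAM-A result.

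Under either route, delete PHQ-9 from the secondary outcomes or add it to the instrument list and schedule. Name the scales to be given at each call in Research Design and Methods and in Medical Monitoring, so that both agree with the table.
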